Postpartum Non-pharmacologic Pain Management – Randomized Controlled Trial

Investigators: [name] (PI), [name], [name], DO, [name]

NCT03903172

Postpartum Non-pharmacologic Pain Management – Study Protocol

Investigators: [name] (PI), [name], [name], DO, [name]

Objective

To examine whether use of an abdominal binder for postpartum patients after vaginal delivery can effectively manage their pain and reduce the need for pharmacologic analgesics

Aims

1. To determine whether use of an abdominal binder on postpartum days zero and one will result in decreased patient pain as measured by pain scores on a visual analog scale of one to ten
2. To determine whether use of an abdominal binder for postpartum patients will reduce the quantity of non-narcotic pain medications given on postpartum day zero and one
3. To determine whether use of an abdominal binder for postpartum patients will reduce the quantity of narcotic pain medications given on postpartum day zero and one

Hypothesis

Use of an abdominal binder postpartum after a vaginal delivery will be associated with lower pain scores and reduced need for pharmacologic analgesics.

Background

A significant part of postpartum care involves management of patients' pain and discomfort. Etiologies of this pain include perineal pain, incisional pain, uterine involution pain, and pelvic girdle and lower back pain. Postpartum pain management primarily focuses on the former three types of pain: perineal, incisional and uterine involution. In a review of the management of postpartum pain, Eshkevari et al¹ discuss several well-established pain management strategies employed for postpartum patients, including ibuprofen and other NSAIDs for uterine involution pain and inflammation; local anesthetics for perineal lacerations or episiotomies; warm or cold compresses for perineal pain; and opioids for post-operative or poorly controlled postpartum pain.

Data regarding management of pelvic girdle and lower back pain is scarce and the limited literature available primarily focus on the pregnant patient. Different proposed treatment or management strategies

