 - o Prospective data collection with hard copy data entry form that includes PHI for participant identification, basic demographic information, delivery information (see separate document), non-pharmacologic pain relief measures used
 - o Electronic medical record review for: pain scores, pain location, medications received
 - Pain score immediately postpartum
 - Pain scores on PPD#0 and PPD#1
 - Patient reported pain locations
 - Quantity of non-narcotic pain medication received on PPD#0 and PPD#1
 - Quantity of narcotic pain medication received on PPD#0 and PPD#1
 - Compliance wearing the abdominal binder
- Risks
 - o Allergic reaction to fabric of abdominal binder
 - o Skin irritation
 - o Increased discomfort or pain with use of abdominal binder
- Mitigation of risks
 - o If participants experience an allergic reaction or skin irritation from the abdominal binder they will be offered symptomatic treatment. Participants in the experimental arm will be encouraged to keep the abdominal binders in place for 24 hours postpartum, but will be permitted to remove the abdominal binder at any time should they find it causing irritation, increased pain or any other adverse reaction.

References

1. Eshkevari, L, et al. "Management of Postpartum Pain." *Journal of Midwifery and Women's Health*, vol. 58, no. 6, 2013, pp. 622–631.
2. Wu WH, et al. "Pregnancy related pelvic girdle pain (PGP), I: terminology, clinical presentation, and prevalence." *European Spine Journal*, vol. 13, 2004, pp. 575–589.

3. Vermani, E, et al. "Pelvic girdle pain and low back pain in pregnancy: a review." *Pain Practice*, vol. 10, no. 1, 2009, pp. 60-71.
4. Mens JMA, et al. "The mechanical effect of a pelvic belt in patients with pregnancy-related pelvic pain." *Clinical Biomechanics*, vol. 21, 2006, pp. 122-127.
6. Gillier, CM, et al. "A randomized controlled trial of abdominal binders for the management of postoperative pain and distress after cesarean delivery." *International Journal of Gynecology and Obstetrics*, vol. 133, 2016, pp. 188-191.
7. Ghana, S, et al. "Randomized controlled trial of abdominal binders for postoperative pain, distress, and blood loss after cesarean delivery." *International Journal of Gynecology and Obstetrics*, vol. 137, 2017, pp 271-276.

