## STATISTICAL ANALYSIS PLAN

**TITLE: Postpartum Non-pharmacologic Pain Management – Randomized Controlled Trial**

**INVESTIGATORS:** [name] (PI), [name], [name], DO, [name]

July 27, 2022

NCT03903172

Statistical analysis will consist of comparison of the study groups (Abdominal binder vs Standard of care) on:

- 1) baseline characteristics including age and baseline pain score.
- 2) study outcomes for average pain score on postpartum day 0 and postpartum day 1.
- 3) postpartum non-narcotic pharmacologic medication use.
- 4) narcotic pharmacologic pain medication used.

Analysis will be as follows:

- 1) Baseline age and postpartum pain scores will be analyzed using Student's T-test.
- 2) Average pain scores on PPD0 and PPD1 will be analyzed using Student's T-test.
- 3) Postpartum non-narcotic pharmacologic medications will be compared using Chi square.
- 4) Post partum narcotic pharmacologic medication use will be analyzed using Fisher's Exact test.

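### Aims 2 and 3 concern the quantity of medication, but SAP items 3 and 4 name only categorical tests on undefined categories and no test of total amounts; the stated 80% power is not shown for those tests

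*SAP*

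**What the plan says.** **Aims (protocol).** Aim 2 is whether the binder will "reduce the quantity of non-narcotic pain medications given on postpartum day zero and one". Aim 3 is whether it will "reduce the quantity of narcotic pain medications given on postpartum day zero and one". The Objective is broader: to "reduce the need for pharmacologic analgesics".

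**Data collection plan (protocol).** The record review extracts "Quantity of non-narcotic pain medication received on PPD#0 and PPD#1" and "Quantity of narcotic pain medication received on PPD#0 and PPD#1".

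**Sample Size Estimation & Data Analysis Plan (protocol).** Pain medication is to be compared in morphine equivalents over the hospital stay, by repeated-measures ANOVA. The sample size is 65 per group, for a medium effect with 80% power at p < 0.05, plus 10 for dropout (140 in total). It is said to cover both pain scores and medication use. No effect metric, test, SD or use rate is given.

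**SAP.** Under "Analysis will be as follows", item 3 reads "Postpartum non-narcotic pharmacologic medications will be compared using Chi square" and item 4 reads "Post partum narcotic pharmacologic medication use will be analyzed using Fisher's Exact test". Neither item gives a category definition, dose, total, morphine equivalent or time window.

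**The concern.** Chi square and Fisher's exact test act on counts in categories. The Aims name an amount. An analyst who follows the SAP must first invent the categories (any use, dose bands or drug types), possibly after seeing the data, and finishes without a test of the amount. The protocol and SAP also name different methods for the same outcome, and neither says which governs.

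At stake are two of the three stated aims. If nearly all women take at least one non-narcotic dose (an assumption), an any-use test could report no difference while the number of doses fell. A reader of the results would also assume that the medication comparisons carry the protocol's 80% power.

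**Working it through.** **1. The outcome, place by place**

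| Place | Medication variable | Window | Method |
|---|---|---|---|
| Protocol, Aims 2 and 3 | Quantity, by drug type | Days 0 and 1 | none stated |
| Protocol, Data collection plan | Quantity, by drug type | Days 0 and 1 | none stated |
| Protocol, Data Analysis Plan | Morphine equivalents | Hospital stay | Repeated-measures ANOVA |
| SAP, items 3 and 4 | Undefined categories | not stated | Chi square; Fisher's exact |

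The first three rows are amounts. The SAP row is not, unless dose bands were meant. Even then Chi square would be coarse and would ignore the order of the bands. If any use versus none was meant, it tests whether a drug was taken. Morphine equivalents give a unit for narcotics only, so the protocol row has no stated unit for Aim 2.

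**2. Reproducing 65 per group**

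Inputs: 80% power and p < 0.05 from the protocol; two-sided testing and d = 0.5 for a medium effect are assumptions.

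- Two means, normal formula: n = 2(1.960 + 0.842)²/d² = 2 × 7.85/0.25 = 62.8, so 63 per group. The noncentral t gives 63.8, so 64. Power at 65 is **80.8%**. This matches the protocol.
- Chi square, 1 df, medium w = 0.3: N = 7.85/0.09 = 87.2, so 88 in total or 44 per group. This does not match.

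The stated size therefore fits a comparison of means. The documents do not show power for the SAP's tests.

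**3. Power of the SAP's tests at 65 per group**

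All use rates below are assumptions, because the documents give none. Chi square (uncorrected) and Fisher come from exact binomial sums over the rejection region; rank-sum comes from simulation.

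*Model A: the binder lowers the amount.* A normal amount is shifted down by 0.5 SD and cut so that non-users are zero: p(binder) = Φ(Φ⁻¹(p(control)) − 0.5). For example, 98% becomes 94.0% and 10% becomes 3.7%.

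| Drug type | Control use | SAP's test on any use | Rank-sum on amount |
|---|---|---|---|
| Non-narcotic | 98% | Chi square 19% | about 79% |
| Non-narcotic | 95% | Chi square 34% | about 79% |
| Non-narcotic | 90% | Chi square 45% | about 79% |
| Narcotic | 50% | Fisher 55% | about 66% |
| Narcotic | 20% | Fisher 34% | about 44% |
| Narcotic | 10% | Fisher 17% | about 29% |
| Narcotic | 5% | Fisher 4% | about 16% |

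Under this model, any/none reaches at most 61% (Chi square) or 55% (Fisher) at any cut. Three, four or five equal dose bands give Chi square about 61%, 57% and 54–55%.

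*Model B: the binder changes only whether a drug is taken.* Users' amounts are lognormal and equal in both groups.

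| Use, control vs binder | Chi square | Fisher | Rank-sum |
|---|---|---|---|
| 98% vs 85% | 82% | 70% | about 25% |
| 50% vs 25% | 85% | 81% | about 82% |

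At w = 0.3 (65% vs 35% use), Chi square has 93% and Fisher 90%.

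The contrast at 98% control use reverses between the models, so the documents support only the statement that power is not shown.

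**The case against.** The other side has five arguments.

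- **Dose bands are not ruled out.** A reader might infer that the SAP compares no amounts at all. It does not say so: Chi square on grouped doses would be a rough comparison of amounts. This stands. What remains is that the categories are undefined and no test of totals is named.
- **The protocol's ANOVA may cover both drug types.** A reader might infer that Aim 2 has no analysis anywhere. But the protocol applies the ANOVA to pain medication without limiting it to narcotics, and the morphine-equivalent label may be loose wording. This stands in part: an analysis can be read into the protocol for Aim 2, but its unit is missing and the SAP does not carry it forward.
- **The window is fixed elsewhere.** The Aims and the collected variables both name days 0 and 1. This largely stands, although the protocol's analysis text uses the hospital stay.
- **The SAP's tests may be adequately powered.** A reader might infer from Model A that they are underpowered. Model B shows the opposite at 98% versus 85% use. This stands in full as a reply to any claim of a general power loss.
- **Any use bears on need.** The Objective speaks of need for analgesics, so an any-use comparison is relevant. It is a fair supportive measure, but it does not replace the quantity named in the Aims.

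It is also tempting to say that changing the narcotic analysis brings no gain in power. Under Model A, rank-sum exceeds Fisher, the test the SAP names (44% vs 34%, 29% vs 17%, 16% vs 4%). Under Model B at 50% versus 25% use they are nearly equal. Neither statement holds generally.

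**Conclusion.** The mismatch is established from the text and needs no assumed rates. Aims 2 and 3 and the collected data are quantities. SAP items 3 and 4 give categorical tests on undefined categories, and they conflict with the protocol's ANOVA. Followed as written, the SAP does not directly answer either aim. Aim 1 (pain scores) is not touched by this point.

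The power part is narrower. The 65 per group corresponds to a two-mean comparison at d = 0.5 (80.8%), and 80% is not shown for Chi square or Fisher. The size and even the direction of any power difference depend on assumed use rates and on whether the binder changes the amount or only whether a drug is taken. A test of totals does not guarantee 80% either: under Model A the narcotic total has about 66% or less when control use is 50% or lower.

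The missing quantity analysis must be fixed; the power statement is a separate reporting gap.

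**What to change.** 1. Make the main analysis of SAP items 3 and 4 one prespecified between-group comparison of each woman's total over days 0 and 1. Use morphine milligram equivalents for narcotics and one measure fixed in advance for non-narcotics, such as number of doses.
2. Use a Wilcoxon rank-sum test, state that it decides the result, and give group summaries of the totals as descriptive.
3. Keep any-use proportions, with Chi square or Fisher's exact test, as supportive, because they bear on need.
4. State that this replaces the protocol's ANOVA for medication, and why. One total per woman leaves no repeated measure, totals are likely to be skewed with zeros, and the Aims name days 0 and 1 rather than the whole stay. Limit the morphine-equivalent wording to narcotics.
5. Restate the 80% power as applying to a d = 0.5 difference in an approximately normal measure such as mean pain score, and not to the any-use tests or to totals with many zeros.

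**Cost.** SAP wording, plus some data handling to turn medication records into totals; the quantities are already in the data collection plan. The main downside is that a dose count treats different non-narcotic drugs and strengths as equal. Rank-sum can also have less power than Chi square if the binder changes only whether a drug is taken, which is a further reason to keep the any-use results.

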the participant. The informed consent form will describe the project goals, length and rational, as well as the types of PHI that will be collected. All participants who agree to participate in the study will sign the informed consent form. All participants will be provided with a copy of the signed consent form.

- Study design & procedures
 - o After signing informed consent, participants will be assigned to the intervention or control group via block randomization
 - o Those participants in the standard of care group will receive routine postpartum care
 - o Those participants in the intervention group will receive an abdominal binder in addition to routine postpartum care
 - Determination of appropriate binder size will be based on a visual assessment of the patient's abdominal circumference
 - o Nursing staff will evaluate participant's pain level using a visual analog scale of 1-10 a minimum of every 4 hours. Patient reported pain score and pain location will be recorded in the participant's electronic medical record. These processes do not deviate from current standards of care and documentation.
 - o Additional non-pharmacologic pain relief measures utilized by patients will be documented on the data collection sheet attached to the patient's chart. These measures include heating pad, ice pack, and tucks pads
 - o All medications received will be documented in the electronic medical record per usual documentation protocols
 - o Nursing staff will document compliance of patient for wearing the abdominal binder, making notes when the binder was removed and if/when it was put back on.
- Sample Size Estimation & Data Analysis Plan
 - o Sample size was estimated using G*Power. In order to detect a difference between groups on pain scores and use of pain medications, we will need to enroll 65 patients per group. This will enable us to detect a moderate difference (i.e., medium effect size) between the groups with a power = 80% and p at <0.05. We will enroll an additional 10 patients to account for dropouts for a total N=140.
 - o The two groups will be compared for 1. reported pain scores (assessed by nursing staff and documented in the EMR) and for 2. pain medications used (morphine equivalent as

recorded in the MAR) for the duration of patients' hospital stay. Repeated measures analysis of variance will be used to determine differences between the groups over time.

- Data collection plan

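### The protocol's 80% power claim extends to medication use, but Fisher's exact test in SAP item 4 does not deliver it for narcotic use at 65 per group, and part of the loss is avoidable

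*SAP*

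**What the plan says.** The protocol has one power calculation, under Sample Size Estimation & Data Analysis Plan. Its stated scope is "In order to detect a difference between groups on pain scores and use of pain medications". The result is that "we will need to enroll 65 patients per group", which is said to be enough to "detect a moderate difference (i.e., medium effect size) between the groups with a power = 80% and p at <0.05". Ten more patients are added for dropout, giving 140 in total. The same section describes the medication outcome as "pain medications used (morphine equivalent as" recorded in the MAR, and the analysis as follows: "Repeated measures analysis of variance will be used to determine differences between the groups over time".

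The SAP's analysis item 4 reads: "Post partum narcotic pharmacologic medication use will be analyzed using Fisher's Exact test". It does not define the categories to be compared. It gives no expected narcotic rate, no effect size for proportions and no power.

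**The concern.** The power claim explicitly covers medication use, so a reader will apply the 80% to item 4. Fisher's test conditions on both margins. With arms of this size its attainable error rate falls below the nominal 5%, most of all when few women use narcotics, and power falls with it.

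Reduced opioid use is part of the trial's stated rationale (Protocol, Background). If use is sparse, Aim 3 turns on a handful of women. A null result would then be read as coming from a comparison with 80% power, which neither document supports.

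**Working it through.** **Inputs from the documents.** 65 per group, 80% power, p < 0.05, a medium effect, Fisher's exact test for narcotic use.

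**Assumptions, because the documents are silent.** Two-sided testing; any versus no narcotic use; medium taken as Cohen's h = 0.5; control rates as listed.

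**1. The plan's own figure.** For two means with d = 0.5, n = 2(1.960 + 0.842)²/0.5² = 62.8, so 63 per group. The t-based version gives 64 per group and 80.8% power at 65. The stated figure therefore reproduces for a continuous outcome.

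**2. Which index for proportions fits.** With h = 2·arcsin√p₁ − 2·arcsin√p₂ = 0.5, the same formula gives 63 per group, close to 65. The chi-square index w = 0.3 gives N = (1.960 + 0.842)²/0.3² = 87.2, so 88 in total, which does not match 130. So h = 0.5 is the natural translation, though still an assumption.

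**3. True size of Fisher's test.** All 66 × 66 tables at 65/65 were enumerated and the binomial probability of p ≤ 0.05 was summed under a common rate. The size is 1.2% at a 5% rate, 2.4% at 10% and 3.0% at 20%, with a maximum of 3.51%. The maximum depends on the split: 4.2% at 66/64 and 4.3% at 64/65.

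**4. Power at 65/65 for h = 0.5.** The binder rate is p₂ = sin²(arcsin√p₁ − 0.25). For p₁ = 0.10, arcsin√0.10 = 0.3218, so p₂ = sin²(0.0718) = 0.005. The last column is Boschloo's unconditional exact test with tables ordered by the two-sided Fisher p-value (critical value 0.0716, maximum size 4.94%).

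| Control rate | Binder rate | Fisher | Boschloo |
|---|---|---|---|
| 10% | 0.5% | 54% | 69% |
| 15% | 2.2% | 67% | 75% |
| 20% | 4.5% | 72% | 77% |
| 30% | 10.5% | 75% | 79% |
| 50% | 26.0% | 77% | 81% |

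Below 10%, Fisher's power is 40% at a control rate of 8% and 22% at 6.25%. If all 140 women were analysed at 70/70, it would be 61% at a 10% control rate and 79% at 50%.

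**5. Why this Boschloo version cannot lose to Fisher.** Fisher's rejection region already has size at or below 5%. Ordering tables by the same two-sided p-value and raising the cut-off until the maximum size reaches 5% can only add tables. At 65/65, 5 versus 0 users gives Fisher p = 0.058 and Boschloo p = 0.043; 12 versus 4 gives 0.059 and 0.043.

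**6. The gain depends on the split.** At a 10% control rate with h = 0.5 (control/binder), Fisher versus Boschloo is 54% versus 69% at 65/65, 56% versus 56% at 66/64, 68% versus 68% at 64/65, 67% versus 75% at 63/67 and 61% versus 74% at 70/70.

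**The case against.** Four objections deserve an answer.

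*The 80% belongs to a different endpoint.* It reproduces for a continuous outcome, and the protocol describes medication use as morphine equivalents. A reader might infer that the documents promise 80% for a yes/no comparison and that the trial's actual power is 54–77%. They do neither. What stands is that the claim names medication use as covered, and nothing shows that it holds for the test that the SAP assigns.

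*Other readings of medium give other answers.* With w = 0.3, Fisher's power is 90–97%. With d = 0.5 on quantity cut to any/none, it is about 17% at a 10% control rate and 55% at 50%. That spread is genuine and is why the figures are conditional. But w = 0.3 does not reproduce 65 per group, and it is out of reach when use is sparse. Even if the binder removed all use, w = √[(p₁/2)/(1 − p₁/2)], which is 0.23 at p₁ = 10% and reaches 0.3 only at about 16.5%.

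*Fisher's test is valid and conventional for sparse counts.* Agreed. A reader might infer an alpha error, or an error rate that can never exceed 3.5%. The first is wrong, and the second holds only at exactly 65/65, which dropout makes unlikely.

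*Boschloo's test does not always help.* Also true in part. At some splits and low rates the gain is about zero. The common version that doubles the smaller one-sided p-value can lose to Fisher when arms are unequal. At 64/65, 10 versus 3 users gives 0.053 against Fisher's 0.044. At 62 control/70 binder with 10% versus 0.5%, its power is 65% against 73%. The version ordered by the two-sided Fisher p-value does not have this defect.

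**Conclusion.** The point holds as an unsupported power statement together with avoidable power loss. With an any/none outcome and h = 0.5, Fisher's power at 65/65 runs from 54% to 77% over control rates of 10–50% and is lower below 10%. It stayed below 80% at every split examined near this size. The size figures follow by enumeration; the power figures rest on assumed rates and an assumed effect index.

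The test choice explains only part of the gap. At 65/65 the better exact test adds about 15 points at a 10% control rate and about 4 points at 20% and above, and it reaches 80% only near a 50% rate. Restating the power claim therefore matters at least as much as changing the test.

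Aim 3 concerns quantity, whereas item 4 names a categorical test with undefined categories. That mismatch is arguably larger, but it is a separate issue.

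**What to change.** - **SAP item 4:** define the yes/no outcome. For that comparison, specify Boschloo's unconditional exact test at two-sided 5%, with tables ordered by the two-sided Fisher p-value, and say that the doubled one-sided version is not meant. Report the risk difference with a 95% confidence interval.
- **Protocol, Sample Size Estimation & Data Analysis Plan:** limit the 80% to the continuous outcome and state d = 0.5, which is the value that reproduces 65. Next to it, give the power of the item 4 test at 65 per group over a range of assumed control rates, with the effect index named.

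The cost is a few sentences, with no added patients or data. The one practical burden is that the exact version must be named and may need a few lines of code, because packaged routines can implement the doubled form. The change does not reconcile Aim 3's quantity with a yes/no test, which has to be settled separately.
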